### C.6.9 Rationale for Selection of Trial Endpoints

Trial endpoints were selected with following considerations:

- Clinically relevant and address important safety and performance aspects of the investigational TAVI device
- Objectively defined and measurable in the majority of subjects
- Consistent with current recommendations for endpoints in TAVI clinical studies and VARC-2

### C.6.10 Multiplicity Considerations

It is recognized that with a multiplicity of tests comes inflation in the chance of a false finding of superiority or non-inferiority. Therefore, for the purpose of seeking approved labeling claims on designated secondary objectives, the following standard will be used: If the primary objective demonstrates non-inferiority, claims will be sought for selected secondary non-inferiority and superiority objectives and for superiority on the primary objective metric. These will be tested via a hierarchical (sequential) order that preserves the overall study-wise type I error rate at the level of 0.05, while requiring all non-inferiority tests to meet a nominal type I error rate of 0.05 and all superiority tests to meet a nominal type I error rate of 0.025. The testing order is specified below. The following objectives are tested in order, and testing continues if and only if all previous objectives have met their designated success criterion.

1. Primary endpoint (non-inferiority)
2. Transvalvular mean gradient at 12 months (non-inferiority)
3. Effective orifice area at 12 months (non-inferiority)
4. Change in NYHA classification from baseline to 12 months (non-inferiority)
5. Change in KCCQ score from baseline to 30 days (non-inferiority)

All of the above are non-inferiority tests and are tested with a type I error standard of 0.05. If all of the above tests meet their success criterion, the type I error rate of 0.05 that is passed on from the above tests will be split equally (using a Bonferroni justification) between the following parallel subfamilies, so that each subfamily is tested using a type I error rate of 0.025:

Subfamily #1: Primary endpoint (superiority)

Subfamily #2: Secondary (superiority) objectives #5–#18 as enumerated below, tested in ordered sequence such that all  $\alpha$  is passed on to subsequent tests if a test criterion is met, while all testing stops if a test criterion is not met. This procedure controls the type I error rate of this subfamily at the level 0.025.

It is not necessary to “pass” all objectives in one subfamily in order to test the objective(s) in the other subfamily. For the purposes of seeking claims, these objectives will only be evaluated once, at the same time as non-inferiority of the primary objective is established. The only exception to this is the primary endpoint superiority test, which carries the possibility of a delayed determination of superiority (as described in Section 4.2.1) and may thus meet its success criterion at a different time.

The remaining secondary objectives may be of interest for scientific or financial reasons but will not be the basis for supporting labeling claims; they are thus outside of the hierarchical testing procedure. Similarly, for those objectives that test non-inferiority, if non-inferiority is established, a test of superiority will also be conducted, but unless specifically itemized in the list, such superiority testing is not part of the hierarchical testing procedure; these superiority tests may be of interest for scientific or financial reasons but will not be the basis for supporting labeling claims.

#### C.6.10.1 Secondary Endpoints Tested to Support Labeling Claims

The following secondary endpoints will be tested, in order, to support labeling claims:

1. Transvalvular mean gradient at 12 months (non-inferiority): TAVI vs. SAVR (secondary objective #12). The hypothesis of interest is

$$H: \mu_{TAVI} < \mu_{SAVR} + 5$$

where  $\mu_{TAVI}$  and  $\mu_{SAVR}$  denote the average mean gradient from at 12 months, measured in mmHg. This objective will be evaluated using a Bayesian version of a two-sample t-test (see Section C.11). The posterior probability  $P(H | \text{data})$  will be calculated and compared to a threshold of 0.95.

2. Effective orifice area at 12 months (non-inferiority): TAVI vs. SAVR (secondary objective #12). The hypothesis of interest is

$$H: \mu_{TAVI} > \mu_{SAVR} - 0.1$$

where  $\mu_{TAVI}$  and  $\mu_{SAVR}$  denote the mean effective orifice area at 12 months, measured in  $\text{cm}^2$ . This objective will be evaluated using a Bayesian version of a two-sample t-test (see Section C.11). The posterior probability  $P(H | \text{data})$  will be calculated and compared to a threshold of 0.95.

3. Change in NYHA classification from baseline to 12 months (non-inferiority): TAVI vs. SAVR (secondary objective #8). The hypothesis of interest is

$$H: \mu_{TAVI} > \mu_{SAVR} - 0.375$$

where  $\mu_{TAVI}$  and  $\mu_{SAVR}$  denote the mean number of classification improvements in NYHA from baseline to 12 months. For subjects with NYHA categories at both baseline and 12 month visit, the NYHA classification improvements will be calculated as  $NYHA_{baseline} - NYHA_{12month}$ . This objective will be evaluated using a Bayesian version of a two-sample t-test (see Section C.11). The posterior probability  $P(H | data)$  will be calculated and compared to a threshold of 0.95.

4. Change in Kansas City Cardiomyopathy Questionnaire (KCCQ) score from baseline to 30 days (non-inferiority): TAVI vs. SAVR (secondary objective #11). The hypothesis of interest is

$$H: \mu_{TAVI} > \mu_{SAVR} - 5$$

where  $\mu_{TAVI}$  and  $\mu_{SAVR}$  denote the mean improvements in the KCCQ score from baseline to 30 days. For subjects with KCCQ score at both baseline and 30 days, the improvement in KCCQ will be calculated as  $KCCQ_{30day} - KCCQ_{baseline}$ . This objective will be evaluated using a Bayesian version of a two-sample t-test (see Section C.11). The posterior probability  $P(H | data)$  will be calculated and compared to a threshold of 0.95.

5. Length of index procedure hospital stay after TAVI vs. SAVR (secondary objective #18). The hypothesis of interest is

$$H: \mu_{TAVI} < \mu_{SAVR}$$

where  $\mu_{TAVI}$  and  $\mu_{SAVR}$  denote the mean length of index hospital stay. This objective will be evaluated using a Bayesian version of a two-sample t-test (see Section C.11). The posterior probability  $P(H | data)$  will be calculated and compared to a threshold of 0.975.

6. Transvalvular mean gradient at 12 months (superiority): TAVI vs. SAVR (secondary objective #12). The hypothesis of interest is

$$H: \mu_{TAVI} < \mu_{SAVR}$$

where  $\mu_{TAVI}$  and  $\mu_{SAVR}$  denote the average mean gradient from at 12 months, measured in mmHg. This objective will be evaluated using a Bayesian version of a two-sample t-test (see Section C.11). The posterior probability  $P(H | data)$  will be calculated and compared to a threshold of 0.975.

7. Effective orifice area at 12 months (superiority): TAVI vs. SAVR (secondary objective #12). The hypothesis of interest is

$$H: \mu_{TAVI} > \mu_{SAVR}$$

where  $\mu_{TAVI}$  and  $\mu_{SAVR}$  denote the mean effective orifice area at 12 months, measured in  $cm^2$ . This objective will be evaluated using a Bayesian version of a two-sample t-test (see Section C.11). The posterior probability  $P(H | data)$  will be calculated and compared to a threshold of 0.975.

8. Change in Kansas City Cardiomyopathy Questionnaire (KCCQ) score from baseline to 30 days (superiority): TAVI vs. SAVR (secondary objective #11). The hypothesis of interest is

$$H: \mu_{TAVI} > \mu_{SAVR}$$

where  $\mu_{TAVI}$  and  $\mu_{SAVR}$  denote the mean improvements in the KCCQ score from baseline to 30 days. For subjects with KCCQ score at both baseline and 30 days, the improvement in KCCQ will be calculated as  $KCCQ_{30day} - KCCQ_{baseline}$ . This objective will be evaluated using a Bayesian version of a two-sample t-test (see Section C.11). The posterior probability  $P(H | data)$  will be calculated and compared to a threshold of 0.975.

9. Days alive out of the hospital at 12 months after TAVI vs. SAVR (secondary objective #10). The hypothesis of interest is

$$H: \mu_{TAVI} > \mu_{SAVR}$$

where  $\mu_{TAVI}$  and  $\mu_{SAVR}$  denote the mean number of days alive out of the hospital at 12 months. This objective will be evaluated using a Bayesian version of a two-sample t-test (see Section C.11). The posterior probability  $P(H | data)$  will be calculated and compared to a threshold of 0.975.

10. Days alive out of the hospital at 24 months after TAVI vs. SAVR (secondary objective #10). The hypothesis of interest is

$$H: \mu_{TAVI} > \mu_{SAVR}$$

where  $\mu_{TAVI}$  and  $\mu_{SAVR}$  denote the mean number of days alive out of the hospital at 24 months. This objective will be evaluated using a Bayesian version of a two-sample t-test (see Section C.11). The posterior probability  $P(H | \text{data})$  will be calculated and compared to a threshold of 0.975.

11. Change in SF-36 Physical Summary Scale from baseline to 3 months: TAVI vs. SAVR (secondary objective #11). The hypothesis of interest is

$$H: \mu_{TAVI} > \mu_{SAVR}$$

where  $\mu_{TAVI}$  and  $\mu_{SAVR}$  denote the mean improvements in the SF-36 Physical Summary Scale from baseline to 3 months. This objective will be evaluated using a Bayesian version of a two-sample t-test (see Section C.11). The posterior probability  $P(H | \text{data})$  will be calculated and compared to a threshold of 0.975.

12. Change in EQ-5D from baseline to 3 months: TAVI vs. SAVR (secondary objective #11). The hypothesis of interest is

$$H: \mu_{TAVI} > \mu_{SAVR}$$

where  $\mu_{TAVI}$  and  $\mu_{SAVR}$  denote the mean improvements in the EQ-5D from baseline to 3 months. This objective will be evaluated using a Bayesian version of a two-sample t-test (see Section C.11). The posterior probability  $P(H | \text{data})$  will be calculated and compared to a threshold of 0.975.

13. Incidence of MACCE at 30 days or hospital discharge, whichever is longer: TAVI vs. SAVR (secondary objective #1). The hypothesis of interest is

$$H: \pi_{TAVI} < \pi_{SAVR}$$

where  $\pi_{TAVI}$  and  $\pi_{SAVR}$  denote the binary rate of MACCE at 30 days or hospital discharge (if longer). The posterior probability  $P(H | \text{data})$  will be calculated and compared to a threshold of 0.975. The statistical method will be the Bayesian version of a comparison of proportions (see Section C.11).

14. Incidence of major vascular complications at 30 days or hospital discharge, whichever is longer: TAVI vs. SAVR (secondary objective #3). The hypothesis of interest is

$$H: \pi_{TAVI} < \pi_{SAVR}$$

where  $\pi_{TAVI}$  and  $\pi_{SAVR}$  denote the binary rate of major vascular complications at 30 days or hospital discharge (if longer). The posterior probability  $P(H | \text{data})$  will be calculated and compared to a threshold of 0.975. The statistical method will be the Bayesian version of a comparison of proportions (see Section C.11).

15. Incidence of major or life-threatening bleeding event at 30 days or hospital discharge, whichever is longer: TAVI vs. SAVR (secondary objective #3). The hypothesis of interest is

$$H: \pi_{TAVI} < \pi_{SAVR}$$

where  $\pi_{TAVI}$  and  $\pi_{SAVR}$  denote the binary rate of major or life-threatening bleeding events at 30 days or hospital discharge (if longer). The posterior probability  $P(H | \text{data})$  will be calculated and compared to a threshold of 0.975. The statistical method will be the Bayesian version of a comparison of proportions (see Section C.11).

16. Incidence of all strokes at 30 days or hospital discharge, whichever is longer: TAVI vs. SAVR (secondary objective #15). The hypothesis of interest is

$$H: \pi_{TAVI} < \pi_{SAVR}$$

where  $\pi_{TAVI}$  and  $\pi_{SAVR}$  denote the binary rate of strokes at 30 days or hospital discharge (if longer). The posterior probability  $P(H | \text{data})$  will be calculated and compared to a threshold of 0.975. The statistical method will be the Bayesian version of a comparison of proportions (see Section C.11).

17. Incidence of moderate/severe aortic insufficiency after TAVI vs. SAVR (secondary objective #12). The hypothesis of interest is

$$H: \pi_{TAVI} < \pi_{SAVR}$$

where  $\pi_{TAVI}$  and  $\pi_{SAVR}$  denote the proportion of subjects with moderate/severe aortic insufficiency at the discharge echo. The posterior probability  $P(H | \text{data})$  will be calculated and compared to a threshold of 0.975. The statistical method will be the Bayesian version of a comparison of proportions (see Section C.11).

18. New pacemaker implant rate for TAVI at 30 days or hospital discharge, whichever is longer (secondary objective #7). The hypothesis of interest is

$$H: \pi_{TAVI} < 30\%$$

where  $\pi_{TAVI}$  denote the binary rate of new pacemaker implants for TAVI at 30 days or hospital discharge (if longer). The posterior probability  $P(H | \text{data})$  will be calculated and compared to a threshold of 0.975. The statistical method will be the Bayesian version of a comparison of proportions (see Section C.11).

Other than the hierarchical testing procedure described above, no further multiplicity adjustments will be made in the analyses of the secondary endpoints. Summary data from other secondary objectives, such as device success and procedural success from secondary objectives #20 and #21, respectively, may be provided in the device labeling. However, no claims of statistical significance or other statistical inference will be made.

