#### Sample Size Justification

The assumed values  $\pi_T = \pi_C = 0.17$  are based on the data published by Iturra et al and CoreValve US Pivotal High Risk study results. As reported in the Iturra paper, the incidence of all-cause mortality at 30 days was 2.8% and the late all-cause mortality Kaplan-Meier rate at 24 months was 12.1%. The overall 24-month all-cause mortality rate was approximately 15%. STS score reported in the Iturra paper ( $5.6 \pm 1.1$ ,  $n=502$ ) was similar to the STS score for subjects currently enrolled in the SURTAVI study ( $5.6 \pm 1.4$ ,  $n=654$ ), and it is believed that the 24-month all-cause mortality rate in SURTAVI will be approximately 15% at 24 months. The major stroke rate was 3.2% for subjects who survived to 1 year in the CoreValve Pivotal High Risk study. The High Risk study enrolled a higher-risk population than SURTAVI, therefore, the major stroke rate in the High Risk study is adjusted downward, and it is believed the disabling stroke rate at 24 months would be approximately 2% in the SURTAVI study. Overall, the estimation of the all-cause mortality or disabling stroke rate at 24 months is 17%.

Although the pre-specified analysis methods are Bayesian, the sample size is guided by a standard frequentist non-inferiority power analysis. Under the assumptions of  $\pi_T = \pi_C = 0.17$ , non-inferiority margin  $\delta=0.07$ , 1:1 randomization,  $\alpha = 0.05$ , and power = 95%, the method of Farrington and Manning as implemented in PASS 2008 indicates that the required sample size for a single-look analysis is 1258. To allow for up to 6% dropout, 1339 subjects must be accrued. Furthermore, to compensate for power lost in a two-look group sequential analysis plan using Pocock-type alpha spending, the sample size would have to be increased by about 12.5%. This leads to an estimated sample size of 1531. Thus a sample size of 1600 mITT subjects should provide ample power for establishing non-inferiority in the primary hypothesis test.

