- The incidence of conduction disturbance requiring permanent pacemaker implantation will be provided at 30 days, 6 months, 12 months, 18 months, 24 months, and annually thereafter up to 5 years, separately for new onset and pre-existing conduction disturbance. The statistical method will be the Bayesian version of a comparison of proportions (with predictions).
8. Change in NYHA class from baseline at 30 days, 6 months, 12 months, 18 months, 24 months, and annually thereafter up to 5 years.
- For each subject with paired data, the number of classes changed from baseline (-3, -2, -1, 0, 1, 2, or 3) will be calculated at 30 days, 6 months, 12 months, 18 months, 24 months, and annually thereafter up to 5 years. The endpoint will be evaluated between groups using a Bayesian version of a t-test.
9. Change in distance walked during 6-minute walk test (6MWT) from baseline to 30 days, baseline to 12 months, and baseline to 24 months.

All subjects who are able to perform the six-minute walk evaluation at the time of the follow-up visit will be included in the analysis.

The endpoint will be evaluated using a Bayesian version of a t-test.

10. Ratio of days alive out of hospital versus total days alive assessed at 12 months and 24 months follow-up.

The proportion of post procedure days alive out of hospital against total days alive will be compared between groups at 12 and 24 months. The numerator will be the number of days alive out of hospital, and the denominator will be the number of post procedure days alive as of the last follow-up date. All hospitalizations will be included in this analysis, including hospitalization for device implant.

In addition, days alive out of hospital will be compared between groups at 12 months and 24 months.

The endpoint will be evaluated using a Bayesian version of a t-test.

11. Quality of Life (QoL) change from baseline at 30 days, 3 months, 6 months, 12 months, 18 months, 24 months, and annually thereafter up to 5 years.

The Kansas City Cardiomyopathy Questionnaire (KCCQ), SF-36, and EuroQoL (EQ-5D) will be assessed at baseline, 30 days, 6 months, 12 months, 18 months, 24 months, and annually thereafter up to 5 years. SF-36 and EQ-5D will also be assessed at 3 months. All subjects completing the questionnaires will be evaluated and the reasons for missing data will be provided.

The endpoint will be evaluated using a Bayesian version of a t-test .

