12. Echocardiographic assessment of prosthetic valve performance at discharge, 6 months, 12 months, 24 months, and annually thereafter up to 5 years using the following measures:

- transvalvular mean gradient
- effective orifice area
- degree of prosthetic aortic valve regurgitation (including transvalvular and paravalvular)

The four echocardiographic measurements will be evaluated at discharge, 6 months, 12 months, 24 months, and annually thereafter up to 5 years. All implanted subjects undergoing echocardiography procedures will be evaluated.

Continuous measures will be evaluated using a Bayesian version of a two-sample t-test. Categorical variables will be evaluated using Bayesian version of a comparison of polytomous outcomes.

Additionally, incidence of moderate/severe aortic insufficiency at discharge will be compared between groups using the Bayesian version of a comparison of proportions.

13. Aortic valve disease related hospitalizations

The number of subjects re-hospitalized after the initial index procedure will be compared at 30 days, 6 months, 12 months, 18 months, 24 months, and annually thereafter up to 5 years.

Incidence of recurrent hospitalization will be provided at 30 days, 6 months, 12 months, 18 months, 24 months, and annually thereafter up to 5 years. The statistical method will be the Bayesian version of a comparison of proportions (with predictions).

14. Cardiovascular deaths and valve-related deaths

The number of subjects experiencing cardiovascular deaths and valve-related deaths at 30 days, 6 months, 12 months, 18 months, 24 months, and annually thereafter up to 5 years. Incidences will be compared between groups. The statistical method will be the Bayesian version of a comparison of proportions (with predictions).

15. Strokes and TIAs

The number of subjects with strokes (of any severity) and TIAs at 30 days, 6 months, 12 months, 18 months, 24 months, and annually thereafter up to 5 years. A separate analysis will be performed for each of the following:

- a composite of all strokes and TIAs
- disabling strokes only
- non-disabling strokes only
- TIAs only

The statistical method will be the Bayesian version of a comparison of proportions (with predictions).

Additionally, incidence of all strokes at 30 days or hospital discharge, whichever is longer, will be compared between groups using the Bayesian version of a comparison of proportions.

16. Peri-procedural Neurological Injury (Stroke, TIA, Encephalopathy)

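### The NYHA and KCCQ labeling tests drop subjects who die before the visit, so they compare survivors rather than the randomized groups and need a death-scored supporting analysis

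*Combined protocol and SAP*

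**What the plan says.** C.6.10.1 defines the NYHA labeling test (test 3, margin 0.375 class) on paired subjects: "For subjects with NYHA categories at both baseline and 12 month visit, the NYHA classification improvements will be calculated as" the baseline class minus the 12-month class. The parent endpoint, number 8 in C.6.8.1, says the same: "For each subject with paired data, the number of classes changed from baseline" is calculated, on a scale from -3 to 3 that has no value for death.

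The KCCQ non-inferiority test (test 4, margin 5 points) and superiority test (test 8) share one rule: "For subjects with KCCQ score at both baseline and 30 days, the improvement in KCCQ will be calculated as" the 30-day score minus the baseline score. For quality of life in general, C.6.8.1 adds that "All subjects completing the questionnaires will be evaluated and the reasons for missing data will be provided".

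C.6.4.2 names mITT as the population for most secondary objectives. C.6.6, on missing data and sensitivity analyses, is limited to the primary objective. Under C.6.10, tests 3 and 4 follow non-inferiority on the primary endpoint and on two echo measures. Both must pass before primary superiority or any of the superiority claims 5 to 18 is tested.

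**The concern.** Death before the visit is an outcome of treatment, not a gap in data collection. Once those subjects are left out, the two groups being compared are no longer the groups that were randomized, whatever the population is called. Tests 3, 4 and 8 then give the same answer however many subjects die in either arm.

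This matters because tests 3 and 4 lie on the path to every superiority claim, and all three results are meant for labeling. Read plainly, a statement that NYHA change is non-inferior at 12 months would be taken to cover everyone treated. The omission can work either way: extra early deaths after SAVR would be just as invisible as extra early deaths after TAVI.

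**Working it through.** **Plan figures reproduced.** The sample size section gives 2.8% mortality at 30 days and 12.1% late mortality to 24 months. Together: 1 - 0.972 × 0.879 = 14.6%, in line with the stated 15% or so. The Farrington-Manning calculation (17% per arm, margin 0.07, one-sided 0.05, power 95%) returns the plan's 1258. No sample size or power is given for the NYHA or KCCQ tests.

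**How many subjects go unscored.** Assume a constant late hazard h = -ln(0.879)/700 = 0.000184 per day.
- By day 30: 2.8%, or 0.028 × 1600 = about 45 subjects.
- By day 365: 1 - 0.972 × exp(-335h) = 8.6%, or about 138 subjects.

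**What the first test lets through.** With Beta(1,1) priors, threshold 0.971, 800 per arm and 136 SAVR events (17%), the largest TAVI count that passes is 162 (20.25%). That is an observed excess of 3.25 points (3.0 at 700 per arm). The normal approximation agrees: 0.07 - 1.896 × 0.0194 = 0.033. For true excesses of 0, 2, 3, 5 and 7 points, a single look passes with probability about 0.97, 0.76, 0.57, 0.19 and 0.03.

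**Effect on the NYHA test.** These inputs are assumptions, not in the documents: baseline mean 2.6, SAVR survivor improvement 1.3, SD 0.85, SAVR 12-month mortality 8%, no other missing data. Death is scored as class IV, or one level below it (V).

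Arm mean = g - q × k, and arm variance = (1 - q) × 0.85² + q(1 - q) × k². Here g is the survivor improvement, q the mortality, and k = g + (death class - 2.6). Pass probability = Φ[(0.375 + difference)/SE - 1.645].

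Worked case: TAVI survivors 0.2 class worse (g = 1.1), 3.3 excess points (q = 0.113), death = V.
- SAVR mean: 1.3 - 0.08 × 3.7 = 1.004. TAVI mean: 1.1 - 0.113 × 3.5 = 0.7045. Difference: -0.2995.
- SE = √[(1.672 + 1.869)/800] = 0.0665.
- Φ(0.0755/0.0665 - 1.645) = Φ(-0.51) = 0.31.
- Paired data only: difference -0.2, SE 0.0447, Φ(0.175/0.0447 - 1.645) = 0.99.

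| TAVI survivors | Excess deaths (points) | Paired only | Death = IV | Death = V |
|---|---|---|---|---|
| equal | 3.3 | 1.00 | 1.00 | 0.98 |
| 0.2 worse | 0 | 0.99 | 0.97 | 0.91 |
| 0.2 worse | 2 | 0.99 | 0.82 | 0.58 |
| 0.2 worse | 3.3 | 0.99 | 0.62 | 0.31 |

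Part of the fall comes from the larger variance once deaths are scored, as the zero-excess row shows. In the 0.2-worse case, the 3.3 excess points themselves move the mean by 0.033 × 2.5 = 0.08 to 0.033 × 3.5 = 0.12 class, or 22 to 31% of the margin.

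**Effect on the KCCQ tests.** Assume baseline 60, improvement 10, SD 24 and death scored 0, so that each death costs 70 points. With survivors equal and 0, 1, 2 or 3 excess points by day 30, the mean moves by 0, 0.7, 1.4 or 2.1. Test 4 then passes with probability 0.98, 0.94, 0.84 or 0.68, against 0.99 throughout on paired data. Superiority test 8 has no margin to absorb a shift. Over baselines 50 to 65 and improvements 5 to 20, one excess point moves the mean by 0.55 to 0.85, or 0.45 to 0.70 of the SE (24 × √(2/778) = 1.22).

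**The case against.** The strongest reply is that nothing in the sequence is tested unless non-inferiority on all-cause mortality or disabling stroke has passed. A reader might infer from the paired-data rule that the labeling sequence cannot see excess deaths. It can: a true 5-point excess would pass that first test only about one time in five. What remains is that the test is a 24-month composite. An early difference in deaths can be offset later, so deaths by 30 days or 12 months are not directly bounded.

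A reader might also infer that excess deaths alone would carry TAVI past the NYHA margin. They would not. With survivors equal, that takes roughly 9 to 16 excess points under class V or IV scoring, far above what the first test tolerates. For KCCQ the figure is 6 to 9 points by day 30, where cited mortality is 2.8% in total.

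Nor does the rule open an easy route to primary superiority: an arm with more deaths is very unlikely to reach a posterior probability above 0.989 on death or disabling stroke. The SF-36 and EQ-5D tests (11 and 12) come only after tests 9 and 10, which compare days alive out of hospital.

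The choice between function in survivors and a composite is a legitimate one, and C.6.8.1 endpoint 5 already combines death with NYHA III or IV, though outside the labeling hierarchy. It is also not shown that those who die would have scored below average. The figures above measure the distance between two estimands, not a proven bias.

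Finally, C.6.10.1 refers to a Section C.11 for its method, and C.6.5.2 refers to the SAP for details. Neither is in the material available, so a rule for death there cannot be excluded.

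**Conclusion.** The point holds for tests 3, 4 and 8: as written, they estimate function in survivors with paired scores and do not respond to deaths. It is a gap in the estimand that is cheap to close, not a failure of the testing sequence.

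It can change a conclusion only in combination. For NYHA that needs TAVI survivors who are also somewhat worse and an excess of deaths near what the first test allows: about 0.99 on paired data against about 0.3 to 0.6 with deaths scored. For KCCQ it needs deaths concentrated in the first 30 days. The 3.3-point case is demanding, since the whole observed 24-month excess, strokes included, is treated as deaths by 12 months. The pass probabilities rest on assumed means, SDs and death scores; over wider inputs, one excess point moves the NYHA mean by 0.010 to 0.040 class.

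**What to change.** For labeling tests 3, 4 and 8:
- State that the paired-data result is an estimate in survivors.
- Pre-specify one supporting analysis of all mITT subjects with death scored worst. For NYHA, score death as class IV and, as a second version, one level below IV. For KCCQ, score death at the lowest value, with a rank-based comparison for superiority test 8.
- Report deaths by arm up to each visit beside both results.
- If the primary objective passes but the death-scored and paired results disagree, word the labeling statement as applying to survivors.

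The supporting analysis should not decide whether testing continues. The 0.375 margin was set for a change scale of -3 to 3, and a rank-based KCCQ comparison has no 5-point margin to meet. The same analysis for tests 11 and 12 is optional; the sponsor would have to state the value given to death, since the documents shown give none. If the SAP or Section C.11 already has a rule for death, a cross-reference in C.6.10.1 is enough.

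The cost is one SAP paragraph and one extra analysis per test, with no new data. The downside is that the death-scored estimate mixes survival with function, so both versions must be shown.

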#### C.6.5.2 Randomization, Sample Size and Analysis Plan

Randomization will follow a 1:1 (treatment:control) allocation ratio and be stratified by site and need for revascularization, using a blocked randomization scheme with blocks of randomly varying sizes. The sample size for the mITT population is 1600 subjects.

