The statistical approach for these analyses is Bayesian. The prior distributions for  $\pi_T$  and  $\pi_C$  in these calculations are Beta (1,1). The threshold  $\Psi$  is designated to be 0.971 for non-inferiority testing and  $\Psi_{\text{SUP}} = 0.989$  for superiority testing; these values are selected by trial-and-error to achieve a type I error (under simulation) of at most 0.05 for non-inferiority testing and at most 0.025 for superiority testing. Of note, establishing  $P(H_{\delta=0} | \text{data}) > \Psi_{\text{SUP}}$  means that superiority has been established to a standard equivalent to a nominal significance level of 0.025 (1-sided), but this does not automatically mean that a labeling claim of superiority is supported. See "Multiplicity Considerations" (Section C.12) for additional requirements regarding labeling claims on secondary objectives.

Further details of planned analyses are provided in the SAP.

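### The NYHA, KCCQ, SF-36 and EQ-5D labeling tests compare raw change scores with no stated baseline adjustment, which gives up precision mainly at superiority gates #8, #11 and #12

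*Combined protocol and SAP*

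**What the plan says.** **Change-from-baseline tests.** C.6.10.1 states the method for each listed endpoint in the same way: "This objective will be evaluated using a Bayesian version of a two-sample t-test (see Section C.11". For KCCQ the outcome is a paired difference: "For subjects with KCCQ score at both baseline and 30 days, the improvement in KCCQ will be calculated as" the 30-day score minus the baseline score. The non-inferiority hypothesis is "H: \mu_{TAVI} > \mu_{SAVR} - 5" at a posterior threshold of 0.95 (#4); superiority uses 0.975 (#8). Test #11 is built on parameters that "denote the mean improvements in the SF-36 Physical Summary Scale from baseline to 3 months", and #12 on the "mean improvements in the EQ-5D from baseline to 3 months". For NYHA, C.6.8.1 (endpoint 8) says: "The endpoint will be evaluated between groups using a Bayesian version of a t-test"; C.6.10.1 #3 uses a margin of 0.375 classes. None of these entries names a covariate or a stratum.

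**Gates.** Under C.6.10, the non-inferiority tests run in fixed order and must all succeed before any superiority test. Subfamily #2 (#5 to #18) stops at the first miss. The objectives are evaluated once, when primary non-inferiority is established; only primary superiority may come later.

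**Baselines.** C.4.1 records NYHA class at screening. C.4.6 and Table 3 record it again after randomization, within 14 days before the procedure. Quality-of-life questionnaires must be completed before the subject is told the assignment (C.4.6; Table 3, note 12).

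**Primary endpoint.** Randomization is to "be stratified by site and need for revascularization". The priors for the two arm rates "in these calculations are Beta (1,1"), with no stratum term. Need for revascularization appears in the poolability and interaction analyses (C.6.11) and the subgroups (C.6.12.1).

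**The concern.** A change score fixes the slope on baseline at 1, so it subtracts the whole baseline, measurement noise included. A regression estimates the slope from the data. Under randomization both target the same between-arm difference, so the margins carry over, but the change score usually has the larger variance.

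What is at stake is the labeling chain. A miss at #8 closes #9 to #18, which include days out of hospital, MACCE, bleeding and stroke. A miss at #11 closes #12 to #18. If primary non-inferiority is declared at the interim, the single evaluation takes place then. SF-36 at 3 months is collected only in selected geographies (C.4.9.2, C.6.13.1), so #11 will rest on fewer than the planned 1600 subjects. C.6.5.2 justifies the sample size for the primary endpoint, and the protocol text reviewed gives no power for these tests.

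**Working it through.** **1. The plan's own figure.** The only sample-size figure is for the primary endpoint. The Farrington-Manning method with rates 0.17 and 0.17, margin 0.07, one-sided 0.05 and power 95% gives 628.56, so 629 per arm and 1258 in total, as stated. Then 1258/0.94 = 1339 and 1339/0.875 = 1531, also as stated. The planned 1600 exceeds this. There is no corresponding figure to reproduce for the change-score tests.

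**2. Variance ratio.** Let the follow-up SD be 1, the baseline SD be k and the correlation be r. Neither k nor r is in the protocol text reviewed; both are assumed.

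- Variance of the change score: 1 + k² − 2rk
- Variance after regression on baseline: 1 − r²
- Difference: (k − r)², which is never negative. The gain is zero only when k = r.

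| r | k = 1: ratio | reduction | k = 0.8: ratio | reduction |
|---|---|---|---|---|
| 0.3 | 0.91/1.40 = 0.65 | 35% | 0.91/1.16 = 0.78 | 22% |
| 0.5 | 0.75/1.00 = 0.75 | 25% | 0.75/0.84 = 0.89 | 11% |
| 0.7 | 0.51/0.60 = 0.85 | 15% | 0.51/0.52 = 0.98 | 2% |

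At k = 0.6 and r = 0.5 the ratio is 0.75/0.76, a reduction of about 1%. With k above 1 the gain is larger than at k = 1.

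**3. KCCQ power** (assumed: follow-up SD 25, r = 0.5, 800 per arm, normal approximation; true difference 0 for #4 and 3 points for #8).

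- Change score, k = 1: SE = 25 × √(2/800) = 1.25. Non-inferiority (#4): 5/1.25 − 1.645 = 2.355, power 0.991. Superiority (#8): 3/1.25 − 1.96 = 0.44, power 0.670.
- Adjusted: SE = 1.25 × √0.75 = 1.083. Power is 0.999 for #4 and 0.791 for #8.
- Change score, k = 0.8: SE = 1.25 × √0.84 = 1.146. Power for #8 is 0.745, so the gain is from 0.745 to 0.791.
- With k = 1, SD 20 to 30 and r 0.3 to 0.7: power for #4 is 0.879 to 1.000 unadjusted and 0.968 to 1.000 adjusted; for #8 it is 0.394 to 0.972 and 0.554 to 0.987.

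**4. NYHA (#3).** With an assumed SD of change of 1.2 and 700 per arm, SE = 1.2 × √(2/700) = 0.064. The margin of 0.375 is then about 5.8 SE.

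**5. SF-36 (#11), illustration.** With an assumed 400 per arm, a true difference of 0.12 SD, r = 0.5 and k = 1, SE = √(2/400) = 0.071 unadjusted and 0.061 adjusted. Power is about 0.40 and 0.50.

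**6. Primary endpoint.** The stratum removes a share w(1 − w)D²/[p(1 − p)] of the variance, with p = 0.17 from C.6.5.2; the share needing revascularization w and the event-rate gap D are assumed.

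- For w of 10% to 30% and D of 5 to 15 points the share is 0.2% to 3.4%. At w = 30% and D = 16 points it is 0.21 × 0.0256/0.1411 = 3.8%.
- Over the first range the single-look N moves from 1258 to between 1256 and 1216, and single-look power at 1600 with threshold 0.971 moves from 0.967 to between 0.967 and 0.971.
- Single-look simulation with w = 20% and stratum rates of 15% and 25% gives a type I error of 0.0290 unadjusted and 0.0302 stratified.

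**The case against.** The strongest reply is that nothing here is an error. A two-sample comparison of change scores is unbiased under randomization, respects the stated margins and controls type I error. That stands: this is a point about efficiency. The size of the gain also depends on k as well as r. Equal SDs cannot be taken for granted, least of all for NYHA, where entry at class II or above restricts the baseline range. At k = 0.8 and r = 0.7 little is left. The direction of the result does not depend on k.

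It is also fair to say that the method may be set out elsewhere. The text reviewed does not contain the cited Section C.11, and C.6.5.2 defers further detail to the SAP. If either already specifies baseline adjustment for these tests, the point falls away.

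Three stronger readings are tempting, and the documents do not support them:

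- **That omitting the revascularization stratum undermines the primary analysis.** It causes no bias and costs 0.2% to 3.8% of variance under the assumptions tried. Site, the other stratification factor, is absent too. A stratified primary model would not be free either: C.6.5.2 says 0.971 and 0.989 were tuned by simulation, so they would need recalibration.
- **That the 6-minute walk is part of the gate problem.** It is secondary endpoint 9 in C.6.8.1 and not in the C.6.10.1 list. Table 3 schedules no walk test before randomization.
- **That all five tests are at risk.** Non-inferiority tests #3 and #4 look well powered without adjustment.

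**Conclusion.** The point holds for NYHA (#3), KCCQ (#4, #8), SF-36 (#11) and EQ-5D (#12): in the text reviewed they are compared as raw change scores with no stated adjustment, which is valid but gives up precision. The variance saving is about 15% to 35% with equal SDs and about 2% to 22% with a baseline SD of 0.8 of the follow-up SD, for assumed correlations of 0.7 down to 0.3. In large samples adjustment does not increase the variance. The practical value is concentrated at #8, #11 and #12. For KCCQ superiority under the central assumptions, power rises from 0.670 to 0.791 (k = 1) or from 0.745 to 0.791 (k = 0.8). The SDs, correlations, true differences and per-arm numbers in the power examples are all assumptions. The primary model needs no change.

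**What to change.** For #3, #4, #8, #11 and #12, replace the t-test on change with a Bayesian normal linear model of the follow-up value on treatment, baseline value and need for revascularization, and state the priors.

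- Keep the margins (0.375 classes for #3, 5 points for #4) and the 0.95 and 0.975 thresholds. For NYHA a lower follow-up class is better, so the inequality reverses when follow-up class is the outcome.
- Name the baseline: the screening NYHA class, which precedes randomization, and the quality-of-life questionnaire completed before the subject is told the assignment.
- Leave the primary Beta(1,1) model and the 0.971 and 0.989 thresholds unchanged. At most, add a risk difference standardized over the revascularization strata as a sensitivity analysis.

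The cost is SAP wording and code. No new data are needed, and the primary thresholds do not have to be re-simulated.
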